9.3.2.2. Effectiveness Outcomes

- **Patient response to treatment regimen:** Response to each treatment regimen will be recorded as a categorical variable:
 - CR; CR with incomplete platelet recovery (CRp); CR with incomplete haematologic recovery (CRi); Partial Remission; Stable Disease; Progressive Disease; Uncertain Response; Other (before evaluation); Not evaluated/unknown

The response to stem cell transplant for relevant patients will be reported separately, again as a categorical variable:

- CR; CRp; CRi; Partial Remission; Stable Disease; Progressive Disease; Uncertain Response; Not evaluated/unknown

The event of veno-occlusive disease (VOD) following stem cell transplant for relevant patients will be recorded as a binary ‘Y’ or ‘N’ variable, where available.

The event of graft versus host disease (GvHD) following stem cell transplant for relevant patients will be recorded as a binary ‘Y’ or ‘N’ variable, where available.

- **Time to subsequent treatment:** Time in days between start of 1L induction treatment and the initiation of the next line of treatment will be reported as a continuous numerical variable.
- **MRD status:** Minimal residual disease status will be reported for each treatment regimen as a categorical variable:
 - Positive, negative, unknown
- **EFS:** Defined as the date of the start of induction treatment for de novo AML to relapse, death from any cause, or failure to achieve any of the following: CR; CRp; CRi
- **RFS:** Defined as the date of the start of first line treatment for de novo AML, to relapse, will be reported as a separate outcome specifically.

- **OS:** Defined as the date of the start of first line treatment for de novo AML, to death from any cause.

Detailed methodology for identifying the effectiveness outcomes of interest will be built in collaboration with the Pfizer team and aligned as closely with ELN 2017 guidelines⁷ were possible, whilst recognising the limitations associated with identifying complex outcomes using routinely collected real-world data. As such, sensitivity analyses will be applied where necessary, with full details to be documented in the SAP.

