Clinical outcomes will be defined using data collected if available. Clinical outcomes to be assessed include treatment response, survival outcomes, time-to event(s), minimal residual disease (MRD) status and post-transplant events.

Data sources: Data will be collected/extracted from a combination of sites and a registry. The sources include: 1 site and 1 registry in Austria (Austrian Myeloid Registry); 3 sites in Belgium; 1 site in Germany.

Study size: This study is purely descriptive and there will be no limit on the sample size in terms of patients meeting the eligibility criteria. Based on initial feasibility assessments, approximately 230 patients are expected to be eligible for inclusion, however this number will vary once sites are finalised.

Data analysis: Frequencies and percentages will be reported for categorical variables, including the percentage of missing/unknown data, while counts, number of missing, means, medians, standard deviations (SDs), standard errors (SEs), first and third quartiles, minimum and maximum values will be reported for continuous numeric variables. Where applicable, all estimates will be described with accompanying 95% confidence intervals (CI). Time to event analyses will be conducted, with Kaplan-Meier (KM) curves and 95% CI estimated for KM curves outputted. Finally, Sankey diagrams will be generated to aid in interpretation of the analysis of treatment patterns.

Data analysis will be aligned with data extracted/collected from all data sets. Where specific variables or outcomes cannot be assessed/described subgroup analyses could be conducted for a subset of patients from certain data sources.

Milestones:

- Feasibility assessment: 31 July 2022
- Start of data collection (planned): 01 November 2023
- End of data collection (planned): 30 April 2024
- Registration in the EU PAS register: EUPAS49268
- Final study report (planned): 06 September 2024

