8. RESEARCH QUESTION AND OBJECTIVES

This study aims to answer the following research question:

How is GO being used in real world clinical practice of de novo intermediate/favourable risk AML patients and what are the outcomes?

Co-Primary objectives

- To describe the patient demographics and clinical characteristics of patients treated with GO in intermediate and favourable cytogenetic risk, de novo AML.
- To describe GO treatment patterns in the study population, including:
 - Combination chemotherapy regimen
 - GO use in induction and consolidation
 - Number of doses of GO
 - Timing of GO doses in 1L treatment
 - GO dosage

Secondary objective

- To describe 1L treatment effectiveness outcomes for the study population, including:
 - Time-to-next treatment
 - Survival (EFS, RFS, OS)

Exploratory objective

- To describe MRD (minimal residual disease) status for the study population.

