9.7. Data Analysis

Detailed methodology for summary and statistical analyses of data collected in this study will be documented in a SAP, which will be dated, filed and maintained by the sponsor. The SAP may modify the plans outlined in the protocol; any major modifications of primary endpoint definitions or their analyses would be reflected in a protocol amendment.

All analyses will be conducted using Stata 17 software, version 17 or the latest available version (StataCorp, College Station, Texas).

The study is not intended to test hypotheses and is primarily descriptive in nature. Frequencies and percentages will be reported for categorical variables, including the percentage of missing/unknown data, while counts, number of missing, means, medians, SDs, SEs, first and third quartiles, minimum and maximum values will be reported for continuous numeric variables. Where applicable, all estimates will be described with accompanying 95% CIs. Time to event analyses will be conducted, with KM curves and 95% CI estimated for KM curves outputted. Finally, Sankey diagrams will be generated to aid in interpretation of the analysis of treatment patterns.

Where missing values are found in a particular variable, these will be reported either as an unknown categorical group or as the number of patients with a missing data point for continuous variables. In cases where there are large amounts of missing data or where the volume of missing data is differential between important clinical/prognostic groups, imputation may be used and reported in a sensitivity analysis with appropriate methods of imputation decided at analysis phase with the lead study analyst. The threshold of missing data which will require imputation and sensitivity analyses will be determined following initial review of the data.

Data analysis will be aligned with data extracted/collected from all data sets. Where specific variables or outcomes cannot be assessed/described subgroup analyses could be conducted for a subset of patients from certain data sources. Details of potential bias in this dataset are detailed in [Section 9.9](#).

In the event of a data source being unable to provide data for ARW led analysis, variables and outcomes will be assessed using aggregated outputs.

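### Time to next treatment is labelled a continuous variable with no censoring rule; summarised literally, it covers only patients who started a next line and is biased short

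*Protocol*

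**What the plan says.** Section 8 opens the secondary objective with "To describe 1L treatment effectiveness outcomes for the study population, including" and lists "Time-to-next treatment" first, as an item separate from survival (EFS, RFS, OS).

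Section 9.3.2.2 defines the outcome in days from start of first-line induction and states that the time to "the initiation of the next line of treatment will be reported as a continuous numerical variable". EFS, RFS and OS, in the same list, carry no such label. The label does appear in section 9.3.2.1, for the intervals between GO doses.

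Section 9.7 says what is done with variables of that type: "counts, number of missing, means, medians, SDs, SEs, first and third quartiles, minimum and maximum values will be reported for continuous numeric variables". Absent values are reported as "the number of patients with a missing data point for continuous variables". The same section also says: "Time to event analyses will be conducted, with KM curves and 95% CI estimated for KM curves outputted". It does not say which outcomes this covers.

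Censoring is mentioned twice. Section 9.2 applies right-censoring to survival outcomes and names OS, EFS and RFS; section 9.9 names OS and EFS. Neither names time to next treatment.

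**The concern.** A patient in continuing remission has no start date for a next line, and neither does a patient who died before one began. If the outcome is handled as section 9.3.2.2 labels it, these patients have no value, and the mean, SD, median and quartiles describe only those in whom the event has already been seen. Early events are over-represented, because a late event is seen only in a patient followed long enough.

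At stake is the interpretation of a named effectiveness outcome. The figure would look like the time for which first-line treatment holds, but it would depend heavily on length of follow-up and respond only weakly to true durability. Section 9.7 also allows imputation where much is missing. That would not suit patients in whom the event simply has not happened.

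**Working it through.** **The plan's own figures.** The protocol gives no figure for time to next treatment. Its only design figure is the expected size, which reproduces from Table 1: 50 + 30 + 50 + 42 + 18 + 40 = 230. There is no hypothesis test and so no power figure to check.

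**Inputs from the protocol.**
- Indexing period 01 April 2018 to 31 May 2023, about 62 months (section 9.2).
- Planned end of data collection 30 April 2024 (abstract and section 6). Potential follow-up from index is then about 11 to 73 months.
- Planned start of data collection 01 November 2023 (abstract). If charts are abstracted then, follow-up is about 5 to 67 months. The table in section 6 puts the start at 01 November 2024, after its own end date, so the abstract's date is used.
- Minimum follow-up 3 months, earlier deaths eligible (section 9.2.1).
- Median EFS 17.3 and 9.5 months and median OS 27.5 and 21.8 months in the reference trial (section 7). Three of these (9.5, 17.3, 27.5) serve only to set a range for an unknown quantity.

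**Assumptions, not in the protocol.** Exponential time to next treatment with true median M; follow-up uniform between a and b months; at first, no deaths before a next line. The medians of 40 and 60 months and the 3-to-36-month window are illustrative.

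**Formulas.** With λ = ln 2 / M:
- Share with an observed next line = 1 − (e^(−λa) − e^(−λb)) / (λ(b − a)).
- The observed-only median m solves: integral from 0 to m of λe^(−λt)·P(follow-up ≥ t) dt = share / 2. Here P(follow-up ≥ t) is 1 for t < a and (b − t)/(b − a) for t between a and b.

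**Worked case: M = 17.3, a = 11, b = 73.**
- λ = 0.693/17.3 = 0.0401.
- Share = 1 − (0.644 − 0.054)/(0.0401 × 62) = 1 − 0.590/2.484 = 0.76.
- At m = 12.0 the integral is (1 − 0.644) + 0.025 = 0.381, which is half of 0.76.
- The reported median would be 12.0 instead of 17.3 months: 1 − 12.0/17.3 = 31% short.

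**Range, follow-up 11 to 73 months.** A simulation of 1,000,000 patients per case agrees. Kaplan-Meier on all patients, censoring those without a next line, recovers the true median.

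| True median (months) | Share with a next line | Observed-only median | Kaplan-Meier median | Shortfall |
|---|---|---|---|---|
| 9.5 | 90% | 8.2 | 9.5 | 14% |
| 17.3 | 76% | 12.0 | 17.3 | 31% |
| 27.5 | 62% | 14.7 | 27.5 | 46% |
| 40 | 49% | 16.6 | 40.0 | 59% |
| 60 | 37% | 18.2 | 60.2 | 70% |

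From the second row to the last, the true median rises by 42.7 months and the observed-only median by 6.2.

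**Shorter follow-up.** At 5 to 67 months the shortfall runs from 20% (7.6 for 9.5) to 72% (16.5 for 60). At 3 to 36 months it runs from 37% (6.0 for 9.5) to 84% (9.7 for 60).

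**Some patients never need a next line.** Let a share c never need one and the others have median 10 months, with follow-up of 11 to 73 months. The population median is (10/ln 2) × −ln((0.5 − c)/(1 − c)): 18.1 months at c = 0.3 and 25.8 at c = 0.4. It is not reached at c = 0.5 or more. The observed-only median is 8.5 months in every case.

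**Deaths before a next line.** With death as a competing event (median 60 months, follow-up 11 to 73 months), the observed-only medians for 17.3 and 27.5 fall from 12.0 and 14.7 to 10.4 and 12.6.

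**The case against.** The best defence is that the protocol does provide for time-to-event analysis. Section 9.7 plans Kaplan-Meier curves and excludes no outcome. The abstract states: "Clinical outcomes to be assessed include treatment response, survival outcomes, time-to event(s), minimal residual disease (MRD) status and post-transplant events". Its time-to-event item is listed apart from survival, and time to next treatment is the natural candidate for it. Section 9.2 also groups time to next treatment with survival when it justifies the 3-month minimum. The label sits in the variables section, where type labels are used loosely: ELN risk group is called both continuous and categorical. Detailed methods are deferred to the SAP.

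Much of this stands. A reader might infer that the protocol has settled on an analysis of patients with a next line only. It has not: a Kaplan-Meier analysis is left open, and no text says outright that patients without a next line are coded as missing. A reader might also take a large shortfall as a fact of the plan. It is not, because every magnitude rests on assumed distributions, and the bias is modest if nearly all patients start a next line. Nor is it only the patients doing best who drop out; those who die before a next line do too. Finally, the observed-only median for next treatment should not be set against a median for next treatment or death, since these are different quantities.

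Deferral to the SAP does not remove the point. The protocol has not left the reporting scale open: it states one that does not fit a censored outcome. The only texts that point the other way do not name this outcome.

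**Conclusion.** Wrong as written, moderate severity. The definition in section 9.3.2.2, read with the summary rule in section 9.7, gives an observed-only summary of a censored outcome. No statement in the protocol assigns this outcome to Kaplan-Meier or gives it a censoring rule. The most lenient reading is still a conflict between a specific definition and a general methods sentence, and an analyst who followed the definition would produce a biased table.

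Under incomplete follow-up of this kind, the direction does not depend on the exact numbers chosen: the literal summary is too short. The size does. It is about 14% to 70% under exponential times with follow-up of 11 to 73 months and true medians of 9.5 to 60 months, and larger with shorter follow-up. Severity stays moderate because the study is descriptive, the co-primary objectives are unaffected, and EFS, which has a censoring statement, also speaks to durability.

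**What to change.** In section 9.3.2.2, remove the continuous-variable label from time to subsequent treatment. There and in section 9.7, state that:
- it is a time-to-event outcome on all included patients, measured from start of induction;
- a patient who has not started a next line is censored at last available data;
- death before a next line follows a stated rule: either cumulative incidence of next treatment with death as a competing event, or Kaplan-Meier for next treatment or death. Either is defensible, but one has to be chosen and named, because they answer different questions;
- any summary restricted to patients with a next line is labelled as such and shown with its denominator.

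Name the outcome in the censoring text of section 9.2 as well. The cost is a few lines of wording. No new data are needed, since section 9.2 already ends follow-up at death, loss of data or end of study.

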Each data source is likely to capture a large proportion of GO-treated patients in that country, hence their selection. The Austrian, Belgian and German centres have been selected as they meet the feasibility requirements (capture the relevant data variables) and due to the sample size of GO patients that they contain. The Austrian Myeloid Registry recruits data on patients with myeloid diseases from 15 Austrian centres (excluding the Medical University of Vienna) with an estimated enrollment of 3000 patients. The eligibility criteria below are largely based upon the recommend use of GO; ensuring that the overall patient sample gathered will be clinically representative of the GO treated population.

The initiation date of 1L treatment within the indexing period will be defined as the index date. De novo AML diagnosis will be captured within the screening questions of the eCRF and fully defined for each data source within the Statistical Analysis Plan (SAP). Baseline patient demographics and clinical characteristics will be evaluated at index. Treatment patterns and effectiveness outcomes will be described throughout the follow-up period. Patients will have a minimum follow-up of 3 months defined as patients with 3 months of data, following the 1L treatment initiation. This will allow for assessment of treatment patterns and early effectiveness outcomes. Follow-up will end with the following endpoints: death, loss of data (eg, transfer to a new hospital) or end of the study period. In order to maximise the follow-up data captured necessary to accurately assess survival outcomes (EFS, RFS and OS), follow-up will extend up until either the last data available for the patient (in Austrian, Belgium, and German sites), or the date of database extraction (in the Austrian Myeloid Registry). Patients who have limited follow-up data which is not sufficient for the assessment of OS and accurate EFS and RFS, will be right-censored for the purpose of survival outcome specific analysis. Patients who die within the 3-month follow-up period would be considered eligible for inclusion in order to evaluate EFS, RFS and OS outcomes.

Figure 1. Study Schematic

Study Schematic–eCRF and secondary data dataset design

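### RFS is defined from start of first-line treatment to relapse alone, with neither death nor remission in the definition, so a Kaplan-Meier curve would describe neither relapse-free survival nor the probability of relapse

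*Protocol*

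**What the plan says.** Section 8 makes RFS part of the secondary objective, grouped with EFS and OS as survival outcomes for the study population. Section 9.3.2.2 defines the three in one list:

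- EFS starts at induction and counts three kinds of event: a relapse, any death, and not reaching CR, CRp or CRi.
- RFS is given as "Defined as the date of the start of first line treatment for de novo AML, to relapse". The sentence goes on to say that it is presented as an outcome in its own right.
- OS has the same origin as RFS and counts every death.

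Section 9.2 states when observation stops: "Follow-up will end with the following endpoints: death, loss of data (eg, transfer to a new hospital) or end of the study period". It also explains why early deaths are kept: "Patients who die within the 3-month follow-up period would be considered eligible for inclusion in order to evaluate EFS, RFS and OS outcomes".

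Section 9.7 gives the method: "Time to event analyses will be conducted, with KM curves and 95% CI estimated for KM curves outputted". It names no competing-risk method. Section 9.3.2.2 leaves detailed outcome methodology and sensitivity analyses to the SAP.

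**The concern.** The protocol names death as an event for EFS and OS but not for RFS, and it names failure to reach remission only for EFS. Read literally, RFS counts relapse and nothing else, in everyone, from the first day of treatment.

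Two groups are then handled badly. A patient who dies without relapse leaves the risk set as if relapse could still have been observed later. A patient who never reaches remission has nothing to relapse from, yet counts as relapse-free until censored. Neither treatment-related death nor refractory disease can lower the curve.

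The text also disagrees with itself. Early deaths are retained so that RFS can be evaluated, but under this definition they contribute no event to it. An outcome that ignores death also sits oddly in a list of survival outcomes. At stake is one of three named survival results in a study intended for publication.

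**Working it through.** **Inputs from the protocol.** The RFS origin and event, the end of follow-up and the estimator are as quoted above, with no restriction to responders. Table 1 gives 50 + 30 + 50 + 42 + 18 + 40 = 230 patients, which matches the stated study size. The protocol states no RFS figure or event rate, so there is no RFS number to reproduce. Every rate below is an assumption.

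**Definitions side by side**

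| Outcome | Origin | Relapse | Death | No CR/CRp/CRi |
|---|---|---|---|---|
| EFS | start of induction | event | event | event |
| RFS | start of first-line treatment | event | not named | not named |
| OS | start of first-line treatment | – | event | – |

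Death ends follow-up and is not an RFS event, so in a Kaplan-Meier analysis it acts as censoring.

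**Step 1: effect of censoring deaths alone.** Let r and d be the 24-month cumulative incidences of relapse and of death without relapse, from a common origin, with constant hazards. Total hazard λ = −ln(1 − r − d)/24; relapse hazard λr = λ·r/(r + d). Relapse-or-death RFS at 24 months is 1 − r − d. Kaplan-Meier with deaths censored gives exp(−24·λr).

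| r, d | Relapse-or-death RFS | KM, deaths censored | Gap (points) | Relapse implied by KM, against r |
|---|---|---|---|---|
| 40%, 20% | 40.0% | 54.3% | 14.3 | 45.7% against 40% |
| 35%, 10% | 55.0% | 62.8% | 7.8 | 37.2% against 35% |
| 35%, 25% | 40.0% | 58.6% | 18.6 | 41.4% against 35% |

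For the first row, λ = 0.9163/24 = 0.0382, λr = 0.0255 and exp(−0.611) = 0.543. The last column shows that the error reverses when relapse alone is the target: Kaplan-Meier then overstates relapse.

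**Step 2: adding non-responders and the earlier origin.** A simulation of 400,000 patients compared the protocol definition (all patients, from treatment start, relapse only, deaths censored) with relapse or death in responders from remission, each at 24 months from its own origin. Assumed: 35% relapse by 24 months after remission, 1.5 months to remission, non-responder median survival 6 months, and potential follow-up uniform over 12 to 72 months.

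| Remission rate | Death in remission by 24 months | As written | Relapse or death, responders | Gap (points) |
|---|---|---|---|---|
| 75% | 5% | 68.6% | 60.0% | 8.6 |
| 75% | 10% | 67.7% | 55.1% | 12.6 |
| 75% | 20% | 65.4% | 45.0% | 20.4 |
| 85% | 5% | 67.3% | 60.0% | 7.3 |
| 85% | 10% | 66.4% | 55.1% | 11.3 |
| 85% | 20% | 63.9% | 45.0% | 18.9 |
| 92% | 5% | 66.6% | 60.1% | 6.5 |
| 92% | 10% | 65.6% | 55.0% | 10.6 |
| 92% | 20% | 63.1% | 45.0% | 18.1 |

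**Step 3: where the gap comes from (85% remission, 10% death in remission).**

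- Relapse-or-death RFS in responders is 55.0%.
- Censoring deaths raises the estimate to 62.8% (+7.8).
- Starting the clock 1.5 months earlier gives exp(−22.5·λr) with λr = 0.01937, or 64.7% (+1.9).
- Keeping non-responders at risk gives 66.4% (+1.7).

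Censored deaths are the largest part here. Across the grid, non-responders add about 1 to 3 points. If they survive longer (median 24 months, 75% remission, 10% death in remission), they add 71.6 − 64.7 = 6.9 points.

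**Step 4: relapse as the target, whole cohort, same scenario.** The true 24-month cumulative incidence from treatment start is 0.85 × (0.35/0.45) × [1 − exp(−22.5 × 0.02491)] = 0.85 × 0.778 × 0.429 = 28.4%. Kaplan-Meier as written implies 100 − 66.4 = 33.6%, about 5 points too high.

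**The case against.** The strongest reply is that the protocol never says deaths are censored for RFS or that non-responders remain at risk. Both follow only when the definition is combined with the follow-up rule and the Kaplan-Meier method. The sentence in section 9.2 about early deaths could mean that death was always intended to count and that the RFS line is an incomplete summary. Detailed methods go to the SAP, which section 9.7 allows to modify the protocol. The words on reporting RFS separately could also signal a deliberate relapse-only outcome beside an EFS that already covers death and refractory disease.

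Part of this stands. The censoring is an inference, and the SAP may repair it. Deaths and refractory disease remain visible in EFS and OS. But origin and event are stated in the protocol itself, and section 9.7 promises an amendment only for major changes to primary endpoints. A SAP correction could therefore leave this text in place. If relapse alone was intended, the label is wrong and, as step 4 shows, so is the estimator.

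A reader might also infer more than the documents support:

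- **That deaths raise the curve.** A censored death only fails to lower it.
- **That the estimate is too high whatever the target.** This holds against relapse or death. For relapse alone, the freedom-from-relapse estimate is too low.
- **That the result could be compared with no RFS from any other source.** This would rest on outside definitions that are not in the documents.

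**Conclusion.** The definition is wrong as written. Relapse as the sole event, treatment start as the origin and no remission requirement do not yield relapse-free survival, and they do not fit the protocol's own reason for keeping early deaths. With follow-up ending at death and Kaplan-Meier estimation, the upward direction against a relapse-or-death RFS is firm. The size is not: 6.5 to 20.4 points at 24 months depends on constant hazards and on assumed relapse, death and remission rates.

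It would be tempting to call this a defect that must be cured before the study can proceed. The documents do not support that. RFS is one secondary outcome in a study without hypothesis tests, and neither the co-primary objectives nor the expected 230 patients depend on it. It should be fixed.

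**What to change.** In section 9.3.2.2, and in the SAP to match, define RFS in patients who achieve CR, CRp or CRi, as time from the date of the first such response to relapse or death from any cause, censored at last documented contact. The section 9.2 sentence on early deaths then holds for patients who die in remission; the others count in EFS and OS.

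If a relapse-only outcome is wanted, rename it and report cumulative incidence of relapse from remission, with death without relapse as a competing event (Aalen-Johansen estimator), not one minus Kaplan-Meier.

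The wording costs a few lines. The practical cost is the response date. Section 9.3.2.2 lists response only as a category, and section 9.3 says the registry's variables are not fully known. A date field must therefore be confirmed in the eCRF and the registry request before data entry. Sections 9.6 and 9.8 say German records cannot be traced back to patients once entered, so a missing date could not be recovered there (about 40 of 230 patients, Table 1).
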